### **8 ANALYSIS SETS**

The following analysis sets will be defined: All Subjects Set, Randomized Set, Full Analysis Set (FAS), Safety Set and Run-in Subjects Set.

The **All Subjects Set** is defined as all subjects who have been randomized or have received at least 1 dose of inhaled study drug.

The **Randomized Set** is defined as all subjects who have been randomized.

The **Full Analysis Set (FAS)** is defined as all randomized subjects who carry the intended homozygous *F508del-CFTR* mutation and have received at least 1 dose of inhaled study drug.

The **Safety Set** is defined as all subjects who received at least 1 dose of inhaled study drug.

The **Run-in Subjects Set** is defined as all subjects who received orkambi during the run-in period.

## 9 STATISTICAL ANALYSIS

### 9.1 General Considerations

All individual subject data for those randomized or exposed to inhaled study drug will be presented in data listings. Study drug exposure, discontinuations and adverse events during the run-in period will be listed. The Schedule of Assessments is provided in Section 12.1. The precision standards are provided in Section 12.7.

**Continuous variables** will be summarized using the following descriptive summary statistics: the number of subjects (n), mean, standard deviation (SD), median, minimum value (min), and maximum value (max).

**Categorical variables** will be summarized using counts and percentages.

**Study periods:** The study period will be divided into 3 segments based on the treatment of inhaled study drug:

- **Pre-treatment period** is defined as the period after the informed consent/assent date and before the initial dosing of inhaled study drug in treatment period 1. For the Orkambi+/HS- subjects, this corresponds to the Screening Period. While for Orkambi-/HS-, Orkambi-/HS+, and Orkambi+/HS+ subjects, it will also include the Run-in Period.
- **Treatment emergent (TE) period**
  - TE period for Treatment Period 1 will correspond to the period from the first dose of inhaled study drug in Treatment Period 1 to 28 days after the last dose of inhaled study drug in Treatment Period 1 and prior to the first dose of Treatment Period 2, or the Safety Follow-up Telephone Contact or Visit, whichever occurs first.
  - TE period for Treatment Period 2 will correspond to data from the first dose of inhaled study drug in Treatment Period 2 through the Safety Follow-up Telephone Contact or Visit, or 28 days after the last dose of inhaled study drug in Treatment Period 2, whichever occurs first.
- **Post-treatment period** is defined as the period after the last date of TE period for Treatment Period 2 to the date of the last study record in the clinical database or the period between the end of TE period for Treatment Period 1 and the start of TE period for Treatment Period 2.

Treatment Period 2. For subjects who do not have Treatment Period 2, the period after the last date of TE period for Treatment Period 1 to the date of the last study record in the clinical database will be considered as post-treatment period.

**Baseline:** For this crossover study, 2 types of baseline will be defined.

- The **study baseline** is defined as the most recent nonmissing measurement (scheduled or unscheduled) collected before the first dose of inhaled study drug in the study. Study baseline will be used for all summaries of demographics, background, and baseline characteristics, ECG, as well as all efficacy data analyses, including the primary efficacy endpoint analysis.
- The **period baseline** is defined as the most recent nonmissing measurement (scheduled or unscheduled) collected before the first dose of inhaled study drug in each treatment period. For Treatment Period 2, the baseline value should be from an assessment measured after the TE period for Treatment Period 1. Period baseline will be used for all safety data analyses except ECG. Since all ECG assessments will be performed 60 ( $\pm$  30) minutes after completion of inhaled study drug dosing except measurements at Screening, the study baseline will be used for analysis for both periods.

**Absolute change from study baseline** will be calculated as post-baseline value - study baseline value.

**Relative change from study baseline** will be calculated as  $100 \times (\text{post-baseline value} - \text{study baseline value})/\text{study baseline value}$ .

**Absolute change from period baseline** will be calculated as post-baseline value - period baseline value.

**Relative change from period baseline** will be calculated as  $100 \times (\text{post-baseline value} - \text{period baseline value})/\text{period baseline value}$ .

**Unscheduled Visits:** Unscheduled visit measurements will be included in listings, for derivation of visit windows and computation of baseline, and for the analysis of maximum/minimum values and maximum/minimum changes from baseline values.

**Visit Windows:** Section 12.2 defines the visit window mapping rules to derive the analysis visits.

Analysis visit selection rules:

- For all efficacy parameters if there are multiple measurements within a visit window, the record at the corresponding scheduled visit will be used. If there is no measurement at the corresponding scheduled visit, then 1) the record closest to the target day will be used; or 2) if there are multiple records with the same distance to the target day, the earliest record will be used.
- For all safety parameters, if there are multiple measurements within a visit window, then 1) the record closest to the target day will be used; or 2) if there are multiple records with the same distance to the target day, the earliest record will be used.

**Incomplete/Missing data:** will not be imputed, unless otherwise specified.

**Outliers:** No formal statistical analyses will be performed to detect and/or remedy the presence of statistical outliers.

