## 7.2 Sample Size and Power

The primary efficacy endpoint is the absolute change in ppFEV1 from study baseline to the Day 28 measurements in each Treatment Period.

The null hypothesis to be tested is that the mean change from study baseline in ppFEV1 to the Day 28 measurements is the same for VX-371 in combination with HS versus HS alone.

To have a feasible sample size and study duration, this study uses a crossover design. Assuming a standard deviation (SD) of 7 percentage points, 50 subjects per sequence (VX-371 + 4.2% HS followed by 4.2% HS; 4.2% HS followed by VX-371 + 4.2% HS) are needed to have approximately 81% power to detect a 3 percentage point treatment difference in the mean absolute change in ppFEV1 from study baseline at Day 28 between VX-371 + HS and HS alone. The study will have approximately 80% power to detect a 3 percentage point (within treatment) change from study baseline at Day 28 in ppFEV1 for VX-371. A 2-sided significance level of 0.05 was used in the sample size calculations. The sample size took into account an assumed dropout rate of 10%.

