### **9.3 Efficacy Analysis**

The primary efficacy objective of this study is to evaluate the efficacy of VX-371+ HS versus HS alone. For efficacy analysis, the statistical inference will be based on change from study baseline. Unless otherwise defined, all efficacy analyses described in this section will be based on FAS. The efficacy analyses will be performed according to the treatment to which the subject was assigned in each period. Data for a period will be used provided that the subject received at least one dose of study drug in that treatment period.

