##### **9.3.1.2 Primary Analysis of Primary Efficacy Endpoint**

The null hypothesis to be tested is that the mean change from study baseline in ppFEV1 at Day 28 is the same for VX-371 with HS versus HS alone.

[figure not shown]
The primary analysis of the primary efficacy endpoint will be based on a mixed-effects model. This model will include the absolute change from study baseline in ppFEV1 at Day 28 as the dependent variable and the following fixed effects: treatment, period and ppFEV1 at study baseline and subject as a random effect. The within-subject covariance will be assumed to have the compound symmetry (CS) structure. Denominator degrees of freedom for the F-test for fixed effects will be estimated using the Kenward-Roger approximation.

[figure not shown]
No imputation of missing data will be performed. Subjects who have data only for one of the periods will have a data structure similar to a parallel-group trial. Assuming that these subjects have dropped out at random, an estimate of treatment effect based on such subjects will be combined with the estimate from subjects who have data in both treatment periods with weights based on the precision of these estimates.

[figure not shown]

[figure not shown]
where “primary efficacy endpoint” is the absolute change from study baseline in ppFEV1 at day 28.

[figure not shown]
Descriptive summary statistics including n, mean, SD, and least-square means (LS means), along with its SE, 95% CI and the within-treatment 2-sided *P* value will be provided by treatment group. The between-treatment LS mean differences [VX-371 + HS versus HS, VX-371 + HS versus VX-371 + placebo, VX-371 + HS versus placebo, and VX-371 + placebo versus placebo] with the corresponding SE, 95% CIs and 2-sided *P* values will be presented. The cumulative distribution of the absolute change from study baseline in ppFEV1 at Day 28 will be plotted by treatment group.

[figure not shown]

[figure not shown]

[figure not shown]

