#### **9.4.7.2 Decline in Predose Spirometry**

The following summaries regarding the decline in predose spirometry will be provided:

- Number and percentage of subjects with  $\geq 10$ ,  $\geq 15$  or  $\geq 20$  percentage points decrease in absolute change from period baseline in ppFEV1 at each post-baseline visit.
- Number and percentage of subjects with  $\geq 0.2$  L decrease in absolute change from period baseline in FEV1 at each post-baseline visit.

Subjects with  $\geq 10$  percentage points decrease in absolute change from period baseline in ppFEV1 or  $\geq 0.2$  L decrease in the absolute change from period baseline in FEV1 will be listed. The listing will include raw values and absolute/relative changes from period baseline in ppFEV1 and FEV1 at each visit from the period in which the decline criteria was met.

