## 12.2 Analysis Visit Windows for Safety and Efficacy Assessments

**Table 12-5 Visit Window Mapping Rules for Efficacy Assessments**

Assessments	Analysis Period	Analysis Visit	Target Study Day	Visit Window (in study days)
[REDACTED]				
• Weight and Height	1	Baseline	1	[screening visit, Day 1]
	1	Day 28	28	[2, 35]
	2	Baseline	1	[end of TE period for first period +1, Day 1]
	2	Day 28	28	[2, 35]
• Spirometry	1	Baseline	1	[screening visit, pre-dose Day 1]
	1	Day 14	14	(1*, 21]
	1	Day 28	28	[22, 35]
	2	Baseline	1	[end of TE period for Period 1+1, pre-dose Day 1]
	2	Day 14	14	(1*, 21]
	2	Day 28	28	[22, 35]

\* Day 1 post-dose measurement (unscheduled) in each period

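### Does the VX-371 + HS versus HS analysis lose worthwhile precision by using study baseline and leaving out the Day 57 baseline?

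*SAP*

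**What the plan says.** The SAP and protocol are consistent. SAP 9.3 states: "For efficacy analysis, the statistical inference will be based on change from study baseline". SAP 9.1 applies study baseline to background summaries and ECG "as well as all efficacy data analyses, including the primary efficacy endpoint analysis", and adds: "Period baseline will be used for all safety data analyses except ECG". Protocol 12.3.1 makes the same split between efficacy and safety, without the ECG exception. The primary model in SAP 9.3.1.2 has "the following fixed effects: treatment, period and" study-baseline ppFEV1, with subject as a random effect and compound symmetry within subject. Protocol 12.3.3.1 agrees.

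Predose spirometry is scheduled at Day 57. Table 12-5, the efficacy window table, maps a Period 2 spirometry baseline with the window "end of TE period for Period 1+1, pre-dose Day 1" (Day 1 of Period 2 is Day 57). Its visible use is in safety: SAP 9.4.7.2 counts subjects whose values meet a set "percentage points decrease in absolute change from period baseline in" ppFEV1. Parts of SAP 9.3 are blacked out, so only the visible text can be judged.

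**The concern.** A crossover earns its precision within subjects, and a good covariate should explain within-subject variation. Study baseline cannot do that for the primary contrast, because it takes the same value in both periods. The period effect removes drift shared by all subjects, but drift specific to one subject between periods stays in the residual. The two predose period baselines are the planned measurements that might absorb some of it. One is already the study baseline, and the other is collected, mapped in the efficacy window table and then apparently left aside. With planned power only a little above 80%, an unused and nearly free gain would matter.

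**Working it through.** **1. The plan's own figure.** SAP 7.2 gives the inputs: "Assuming a standard deviation (SD) of 7 percentage points, 50 subjects per sequence", a 3-point difference, two-sided 0.05 and 10% dropout. Sequences 1 and 2 hold 100 subjects, 90 after dropout. Reading 7 as the within-subject SD per measurement, the SD of a paired difference is 7 × √2 = 9.9.

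- SE = 7 × √(2/90) = 1.043
- Noncentral t on 88 df, noncentrality 3/1.043 = 2.875: power 81.2%, against about 81% stated.

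Reading 7 as the SD of the paired difference would give 98%, which does not match. The stated power therefore assumes no help from any baseline.

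**2. Does study baseline cancel?** For a subject with baseline B, (Y1 − B) − (Y2 − B) = Y1 − Y2, and the covariate contributes β(B − B) = 0. A fit to simulated complete pairs confirms it: the contrast was −0.6365 with study baseline, without it, and after subtracting a random number per subject. Cancellation costs the contrast nothing.

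Study baseline does matter elsewhere. With about 10% of Period 2 missing, estimates with and without it differed (0.104 and −0.149). In a simulated four-sequence trial the SE of VX-371 + HS minus placebo fell from 1.438 to 1.345 when it was included. SAP 9.3.1.2 reports that contrast and the within-treatment means.

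**3. What could the Day 57 value add?** Let r be the correlation between the difference in period baselines and the difference in Day 28 outcomes. This is an assumption, as the documents give no value. Keep the outcome, and add each period baseline's deviation from the subject's mean of the two. Counting the expected cost of estimating the slope,

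SE(r) = 1.043 × √(1 − r²) × √(1 + 1/86), on 87 df.

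| r | SE | Power |
|---|---|---|
| no term | 1.043 | 81.2% |
| 0 | 1.050 | 80.7% |
| 0.22 | 1.024 | 82.6% |
| 0.33 | 0.991 | 85.0% |
| 0.45 | 0.937 | 88.6% |
| 0.50 | 0.909 | 90.4% |

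Break-even is at r of about 0.11; below that the term loses power.

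**4. How large could r be?** Predose values fall on Days 1, 28, 57 and 84. Let V be the within-subject variance, of which a share s is serially correlated and the rest is visit noise, with C(d) = s × V × exp(−d/τ). Then

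r = [2C(27) − C(29) − C(83)] / [2V − 2C(56)].

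The term in C(29) keeps r small: the Period 1 outcome lies 27 days from its own baseline and only 29 days from the Day 57 baseline. Example with s = 0.75, τ = 84 days, V = 1: C(27) = 0.544, C(29) = 0.531, C(56) = 0.385, C(83) = 0.279, so r = (1.088 − 0.531 − 0.279)/(2 − 0.770) = 0.226.

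Over τ from 7 to 365 days:

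| Serial share s | Largest r | Change in power (points) |
|---|---|---|
| 25% | 0.06 | a loss at every τ tried, at most about 0.5 |
| 50% | 0.13 | about −0.5 to +0.2 |
| 75% | 0.23 | about −0.5 to +1.5 |
| 100% (no visit noise) | 0.48 | about −0.5 to +8.6 |

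If compound symmetry extended to the baselines, r would be 0.

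**5. What would the term cost?** The planned contrast needs Period 1 treatment to have worn off by Day 84, 56 days after the Day 28 dose. The adjusted contrast also needs it gone by Day 57, 29 days after. With equal variances the slope equals r, and a 1-point carry-over seen only at Day 57 in one sequence moves the estimate by about r/2: 0.165 at r = 0.33 and 0.25 at r = 0.5. Simulation agrees (3.02 to 3.17, and 2.99 to 3.24). The planned model is untouched by such a carry-over.

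**6. Change from period baseline as the outcome.** This is worse. Under compound symmetry it doubles the variance and power falls to 52%; with a visit-to-visit correlation of 0.5 the ratio is 1.5 and power 64%. Keeping change from study baseline is the sounder outcome.

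**The case for a change.** The strongest reply is asymmetry: a useless term costs about 0.5 points of power, while a good one could return 8 or 9. Values within a period may correlate more than values across periods. With correlations of 0.9 within and 0.8 between, the variance ratio is 0.75 and power about 90.7% (slope cost not counted). Washout may be extended for infection or exacerbation (Protocol 8.1.3.2), and a subject who misses the Day 57 criteria may still continue after discussion (Protocol 8.1.3.3), so some subject-specific drift is possible. A simulated null trial kept type I error at 5.0% with the term.

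The arithmetic stands, and under those correlations the gain would be real. What does not stand is the premise that they are likely. Nothing in the documents gives them, and Protocol 8.1 and 8.1.3.3 limit such drift through stable Orkambi, aligned antibiotic cycles and entry criteria for Period 2. The low cost is also not the whole price:

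- The primary estimate would lean on the judgement in Protocol 8.2.1 that a 28-day washout returns subjects to baseline, at a time point where the planned model does not need it.
- Subjects without a usable Day 57 value would need a fill-in rule, against the SAP 9.1 default that missing data "will not be imputed, unless otherwise specified".
- Protocol 11.5.1 allows a single post-bronchodilator test after a pre-bronchodilator Day 1, which would weaken the covariate.

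A supportive analysis with the term would be harmless, but it would change no primary result, and the blacked-out parts of SAP 9.3 may already hold something of the kind.

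**Conclusion.** The concern does not hold. Study baseline does cancel from the primary contrast for complete pairs, and the visible efficacy text does not use Day 57. Neither fact biases the estimate, weakens the test or undermines the stated power: 81.2% is reached without either. Under serial drift with at least a quarter of within-subject variance as visit noise, the forgone precision is worth about -0.5 to +1.5 points of power. Larger gains require nearly noise-free spirometry with slow decay, or a large subject-by-period shift.

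These sizes rest on 90 complete pairs, a within-subject SD of 7 and assumed exponential decay of correlation; r itself cannot be taken from the documents. Given the added dependence on full washout by Day 57, whether to include the term is a matter on which statisticians may reasonably differ. The plan made its choice in advance and kept to it in both documents.

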#### **11.6.2.1 Elevation of Liver Function Test Parameters**

It is strongly recommended that subjects with new ALT or AST elevations of  $\geq 3 \times$  ULN and clinical symptoms be followed closely, including repeat confirmatory testing performed by the central laboratory within 48 to 72 hours of the initial finding and subsequent close monitoring of ALT and AST levels, as clinically indicated. If a subject cannot return to the site for liver function testing, a local laboratory may be used. Elevations in LFTs at the local laboratory must be reported immediately to the medical monitor, and the subject must have the tests repeated and sent to the central laboratory as soon as possible (ideally within 48 to 72 hours).

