#### **11.6.2.2 Hyperkalemia**

Subjects with a potassium level that is  $\leq 0.4$  units below the ULN at the Day 1 or Day 57 Visit will be required to have a blood sample collected for a repeat evaluation of plasma potassium within 7 ( $\pm 2$ ) days.

The standard of care for management of hyperkalemia should be applied. A thorough investigation of potential causes should be conducted, and the subject's potassium level should be followed closely.

If hyperkalemia occurs, inhaled study drug should be interrupted until the plasma potassium has stabilized in the normal range. If no convincing temporary or possibly reversible alternative etiology (e.g., oral intake of potassium, acute renal failure, metabolic acidosis, uncontrolled diabetes mellitus, admission of repeated fist-clenching during phlebotomy, hemolyzed sample) for the elevated potassium is identified, study drug treatment must be discontinued regardless of whether the level has improved; this decision should be made in consultation with the medical monitor. Subjects in whom treatment is discontinued for elevated potassium should have their potassium levels monitored closely until levels normalize or return to baseline.

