#### 9.4.2 Clinical Laboratory

For treatment emergent laboratory measurements, the raw values and change from period baseline values of the continuous laboratory continuous laboratory measurements (chemistry, hematology, and coagulation) will be summarized in SI units using descriptive statistics by treatment group at each scheduled time point. Urine sodium to potassium ratios will be summarized by treatment group.

The number and percentage of subjects with abnormal high (>ULN) hematology and chemistry values will be summarized by visit, as will the number and percentage of subjects with abnormal low (<LLN) hematology and chemistry values.

The number and percentage of subjects with laboratory measurements meeting the threshold analysis criteria during the TE period will be presented. The threshold analysis criteria are provided in Section 12.5 (Table 12-8 Threshold Criteria for Laboratory Tests).

The incidence of LFTs meeting the threshold analysis criteria during the TE period against the period baseline threshold criteria will also be summarized by treatment group (only worsening of the shift from period baseline will be presented).

Mean values ( $\pm$  SD) will be plotted against visit for plasma potassium, ALT, AST, alkaline phosphatase, GGT, and total bilirubin.

A listing of subjects with elevated liver function test (LFT, alanine aminotransferase [ALT]>3 Upper Limit Normal [ULN], aspartate aminotransferase [AST]>3 ULN, serum alkaline phosphatase [ALP]>1.5 ULN, direct bilirubin>1.5 ULN, and total bilirubin>1.5 ULN) results during the TE period will be presented. The listing will include all parameters of the LFT assessment at all visits.

A listing of subjects with elevated plasma potassium level at any time point during the TE period will be provided. The listing will include all plasma potassium measurements at all visits.

Results of urinalysis and serum pregnancy tests will be listed in individual subject data listings only. In addition, a listing containing individual subject laboratory measurements outside the reference ranges will be provided. This listing will include data from scheduled and unscheduled time points.

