**Note:**

1. All assessments including early termination visits, safety follow-up and unscheduled visits will follow the individual visit window to be mapped to individual visits.
2. Spirometry and vital sign assessments (heart rate, systolic blood pressure and diastolic blood pressure) taken at unscheduled visits or early termination visit or safety-follow-up visits will be considered as predose measurements and follow the visit window mapping rules to derive analysis visit.

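### For safety data the SAP takes the record closest to the target day with no preference for the scheduled visit, so a retest can replace an early abnormal potassium or ALT/AST value in the by-visit summaries

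*SAP*

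**What the plan says.** SAP Section 9.1 gives two different rules for several records in one visit window.

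- Efficacy: "the record at the corresponding scheduled visit will be used". Closeness to the target day matters only when that record is missing.
- Safety: "For all safety parameters, if there are multiple measurements within a visit window, then 1) the record closest to the target day" is taken, and the earliest record if two are equally close. Scheduled status plays no part.

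Unscheduled records are eligible. Section 9.1 says: "Unscheduled visit measurements will be included in listings, for derivation of visit windows and computation of baseline". The note under Table 12-6 adds: "All assessments including early termination visits, safety follow-up and unscheduled visits will follow the individual visit window to be mapped to individual visits". For serum and plasma chemistry, Table 12-6 sets the Day 14 window from after Day 1 to Day 21 and the Day 28 window from Day 22 to Day 35. Neither window requires the subject to be on drug at sampling.

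SAP Section 9.4.2 builds several outputs by visit: raw values, changes from period baseline, mean plots for potassium and ALT among others, and counts in which "abnormal high (>ULN) hematology and chemistry values will be summarized by visit".

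The protocol describes how repeat tests arise and when drug stops.

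- Section 11.6.2.1 strongly recommends, for new ALT or AST elevations of at least 3 x ULN with clinical symptoms, "repeat confirmatory testing performed by the central laboratory within 48 to 72 hours of the initial finding". Interruption is mandatory only at higher or combined criteria: at least 8 x ULN; at least 5 x ULN for more than 2 weeks; or at least 3 x ULN with bilirubin at least 2 x ULN and/or jaundice.
- Section 9.5 leaves a confirmatory potassium to the investigator and gives no timing. Section 11.6.2.2 asks for close follow-up and says that in hyperkalemia "inhaled study drug should be interrupted until the plasma potassium has stabilized in the normal range".
- Table 3-3, footnote t, makes the dose at the Day 28 or Day 84 visit the last inhaled dose of the period.

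**The concern.** A repeat test prompted by an abnormal result is not a random extra record. When such a retest competes with the scheduled value on closeness alone, whether the scheduled value survives depends partly on what it showed. If the retest is lower, because the abnormality was transient or because inhaled drug had been stopped, the by-visit displays lean toward normal. The treatment with more abnormal values would have more of them replaced, so a real difference would look smaller in those displays.

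Safety is a primary endpoint, including plasma chemistry (Protocol Section 7.1). Protocol Section 5.1 names hyperkalemia as a limitation of amiloride, the parent of this drug class. SAP Section 9.4 plans descriptive safety analysis only, so the tables and plots are themselves the evidence. A by-visit table could also show a normal value where the threshold table counts an elevation for the same subject.

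**Working it through.** The plan gives no figure for this point, so the check applies its rule to every permitted visit day.

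**Inputs**
- Target days 14 and 28 within each period; windows as in SAP Table 12-6.
- Permitted scheduled days: Day 14 ± 3, i.e. Day 11 to 17 (7 days); Day 28 − 2, i.e. Day 26 to 28 (3 days) (Protocol Table 3-3). Day 70 and Day 84 are the same within-period days.
- Retest lag L in days after the scheduled sample: 2 to 3, from the 48 to 72 hours in Protocol Section 11.6.2.1, counted from the sample. For potassium no lag is stated, so other values are shown as an assumption.

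**Rule.** For a scheduled sample on day v and target t, the retest is chosen if |v + L − t| < |v − t|. A tie keeps the scheduled sample because it is earlier. For v before t this reduces to L < 2(t − v). For v on or after t it never holds, because a later retest is always farther away.

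| Scheduled day | t − v | Lags that displace it |
|---|---|---|
| 11 | 3 | 1 to 5 |
| 12 | 2 | 1 to 3 |
| 13 | 1 | 1 |
| 14 to 17 | 0 or less | none |
| 26 | 2 | 1 to 3 |
| 27 | 1 | 1 |
| 28 | 0 | none |

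**Share of allowed visit days displaced, given a retest at that lag**

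| Lag | Day 14 visit | Day 28 visit |
|---|---|---|
| 1 day (assumed) | 3/7 = 43% | 2/3 = 67% |
| 2 to 3 days | 2/7 = 29% | 1/3 = 33% |
| 4 to 5 days (assumed) | 1/7 = 14% | 0/3 = 0% |

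Read as event shares, these would also need visits spread evenly over the allowed days.

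**Example.** Potassium is high on Day 11 (distance 3), inhaled drug is interrupted, and a repeat on Day 14 (distance 0) is normal. The Day 14 analysis value is the normal, off-drug one. At the end of a period no interruption is needed: if the Day 28 visit takes place on Day 26, its dose is the last, and a repeat on Day 28 is off inhaled drug.

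**Required potassium repeat.** A borderline Day 1 or Day 57 potassium must be repeated within 7 (± 2) days, so by within-period Day 1 + 9 = 10 at the latest. Its distance from Day 14 is at least 4, while a scheduled sample on Day 11 to 17 is at most 3 away. This repeat never displaces a scheduled value.

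**With the efficacy order.** At lags of 2 and 3 days, the present rule replaces the scheduled value in 4 of 14 visit-day and lag combinations for Day 14, and in 2 of 6 for Day 28. With the scheduled record first, both counts are 0.

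**The case against.** The strongest case is that this is a legitimate convention. The rule is explicit, prespecified and blind to treatment, and no hypothesis test depends on it. The safety signal is also well covered elsewhere. In SAP Table 12-8 the hyperkalemia and ALT/AST thresholds start just above ULN, and they are tabulated over the whole treatment-emergent period. Section 9.4.2 lists every subject with an elevated potassium, showing all measurements, and lists elevated liver tests at all visits. Section 9.1 keeps unscheduled values in the maximum/minimum analyses. Section 9.4.1.7 summarises hyperkalaemia adverse events. All of this stands, and it limits the point to by-visit displays.

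The triggers are also narrower than they might look. A reader might infer that the protocol requires these retests. It does not: the ALT/AST retest is a recommendation with two conditions, and the potassium retest is discretionary. Nor is every retest off drug, since most ALT/AST elevations would not meet an interruption criterion, and nothing shows that ALT has recovered within 72 hours.

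The lag may be longer than assumed. The 48 to 72 hours run from detection of the elevation. If that means the reported central laboratory result, and turnaround is 1 to 2 days (an assumption), the lag is 3 to 5 days and the shares become 14% to 29% for Day 14 and 0% to 33% for Day 28.

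Finally, putting the scheduled visit first is not free. Protocol Section 11.6.2.2 lists hemolysis and fist-clenching as causes of a high potassium, and a spurious scheduled value could be kept over a sound repeat. That objection shapes the fix below.

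**Conclusion.** The point holds as a narrow one. The safety rule allows a retest prompted by an abnormal result to replace that result in by-visit means, changes from period baseline, plots and counts above ULN. With a 2 to 3 day lag it affects scheduled visits on Day 11 or 12 (2 of 7 allowed days) or Day 26 (1 of 3), and never a visit on or after the target day. A shift toward normal further assumes that the retest is lower than the value it replaces.

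Two stronger conclusions are tempting. One is that about 30% of abnormal values would be lost; the shares are conditional on a retest and count permitted days, and the documents give no rate of abnormal values or retests from which to estimate affected subjects. The other is that a hyperkalemia signal could disappear from the report or that a VX-371 effect would be diluted by a known amount; the treatment-emergent outputs retain every displaced value, and no size of dilution can be derived. This is a cheap improvement to descriptive tables, not a threat to the safety conclusions.

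**What to change.** In SAP Section 9.1, give safety parameters the same order as efficacy parameters. Within a window, use the valid record from the corresponding scheduled visit. If it is missing, or documented as an invalid sample (for example hemolyzed), use the record closest to the target day, and then the earliest. Keep unscheduled records in the maximum/minimum, threshold and listing outputs as now planned.

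The cost is one sentence and a small programming change before database lock; the logic is already specified for efficacy, and no clinical procedure changes. Two limits remain. A spurious scheduled value that nobody recognises would stay in the by-visit tables in place of its repeat. And the change does not remove off-drug scheduled values, such as a Day 28 sample from a subject interrupted after Day 14.
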